### 7.2.2 During 6MWT

During each 6MWT, the following will be measured:

- SpO2
- Time to participant's first rest, if applicable
- Distance at point of participant's first rest, if applicable
- Number of rest times, if applicable
- 6MWD

If the participant uses walking aids (cane, walker, etc.), these aids should be used during each 6MWT.

Trained study staff will walk alongside the participant for each 6MWT. This study representative will carry the SpO2 monitor, and monitor the participant during the walk, assessing for any variables that may require the participant to rest or terminate the test (eg: study representative may terminate the 6MWT if the participant's SpO2 is below 80%).

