### 10.2 Analysis Populations

The populations are defined as follows.

- The Intent-To-Treat (ITT) is defined as all patients who meet the inclusion/exclusion criteria and begin the first 6MWT.
- The Completed Cases (CC) population is defined as all patients in the ITT population who complete both the first and second 6MWTs.

The primary endpoint analysis will be based on the CC participant population. A participant may rest during the 6MWT and still complete the test, however if the participant stops completely then the 6MWT will be considered incomplete. A sensitivity analysis of the primary endpoint will be generated for the ITT population. The ITT population may contain some participants who complete the first study 6MWT but not the second study 6MWT. This will require the use of imputation methods for missing values which are documented in Section 10.9.

All safety analyses will be generated for participants in the ITT population. All secondary endpoints will be generated using the CC population.

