### 10.9 Handling of Missing Values

The primary endpoint analysis will be based on the CC population. A sensitivity analysis will be done using the ITT population and a mixed-effects cross-over analysis. The mixed-effects analysis uses maximum likelihood to estimate parameters when there are missing values and is appropriate when data is missing at random (MAR).

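### The completers-only primary set can drop a participant because of a low value of the primary outcome, and no rule says how a stopped walk is scored

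*Combined protocol and SAP*

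**What the plan says.** Section 10.1 makes mean SpO2 during the walk the primary endpoint, tested against a margin of 2 points at one-sided 0.025. Section 10.2 defines ITT as eligible participants who begin the first walk, and Completed Cases (CC) as those among them who finish both walks. It then states: "The primary endpoint analysis will be based on the CC participant population". Resting is allowed, "however if the participant stops completely then the 6MWT will be considered incomplete".

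Under Section 7.2.2 the "study representative may terminate the 6MWT if the participant's" SpO2 is below 80%. Section 9.1.1.3 has the session stopped on signs of distress.

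For the back-up analysis, Section 10.2 says: "A sensitivity analysis of the primary endpoint will be generated for the ITT population". It adds: "The ITT population may contain some participants who complete the first study 6MWT but not the second study 6MWT", and "This will require the use of imputation methods for missing values which are documented in Section 10.9". Section 10.9 names no imputation method. It says only that "The mixed-effects analysis uses maximum likelihood to estimate parameters when there are missing values", and calls this suitable under missing at random (MAR). Neither section says what value a stopped walk takes, or whether readings taken before the stop are used.

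**The concern.** The variable that can end a walk is the variable being tested. If a walk is ended for low SpO2, it is incomplete, the participant leaves CC, and a low value of the primary outcome has decided who is analysed. The trial's conclusion rests on one lower bound compared with −2. If low-SpO2 stops are more frequent on Mobi, the worst Mobi results drop out and a device that is truly 2 points worse passes too often. If they are more frequent on the cylinder, the test becomes conservative and the sponsor loses power. With no scoring rule in the plan, the choice could be made after the data are seen.

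**Working it through.** **Inputs from the plan (Sections 10.1 and 10.4).** Margin 2; one-sided alpha 0.025; SDs 3.5 (concentrator) and 2.2 (cylinder); r = 0.2; 30 evaluable and 32 enrolled. **Assumed:** walk means, the shape of the SpO2 fall, and how often staff act.

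**1. The plan's sample size reproduces.** SD of the difference = √(3.5² + 2.2² − 2×0.2×3.5×2.2) = √14.01 = 3.74. With a noncentral t on n − 2 df, power is 79.3% at n = 29 and 80.7% at n = 30. Then 30/0.95 = 31.6, so 32. The arithmetic is not at fault.

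**2. Mechanism in closed form.** Suppose a walk is lost when its mean is below 80, with Mobi mean 86, cylinder mean 88 and the plan's SDs. For Mobi, (86 − 80)/3.5 = 1.714, so about 4% of walks are lost; almost no cylinder walks are. The mean of the retained Mobi walks rises by 3.5 × φ(1.714)/Φ(1.714) = 3.5 × 0.0918/0.9567 = 0.34. Through the correlation, their cylinder partners rise by 0.2 × 2.2 × 0.096 = 0.04. The CC difference is −2 + 0.34 − 0.04 ≈ −1.71 instead of −2.

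**3. Effect on the test** (same rule, n = 32, true difference −2, 40,000 simulated trials; 2.4–2.6% error with all walks kept):

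| SDs Mobi/cylinder | Walks stopped, Mobi/cylinder | CC error if staff always act | Half the time | One time in four |
|---|---|---|---|---|
| 3.5/2.2 | 4% / 0% | 6.0% | 4.0% | 3.1% |
| 3.5/2.2 | 13% / 0.3% | 18.4% | 6.9% | 4.3% |
| 2.9/2.9 | 1.9% / 0.3% | 3.4% | – | – |
| 2.9/2.9 | 8.4% / 1.9% | 6.2% | – | – |
| 2.2/3.5 | 3.5% / 4.4% | 1.5% | – | – |

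Stopped percentages are for staff always acting.

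**4. Within-walk model.** Readings every 10 s start at 93% and fall exponentially (1-minute time constant) with autocorrelated noise. A walk ends at its first reading below 80. Means are Mobi 88 and cylinder 90, with 10,000 trials. Error with all walks complete is 2.4–2.9%.

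| SDs | Stopped, Mobi/cylinder | CC | ITT, pre-stop readings discarded | Mean to the stop | Last reading carried forward |
|---|---|---|---|---|---|
| 3.5/2.2 | 9.4% / 0.2% | 13.0% | 16.3% | 5.8% | 3.1% |
| 2.9/2.9 | 5.6% / 1.2% | 4.9% | 5.7% | 3.6% | 2.7% |
| 2.2/3.5 | 2.0% / 3.0% | 1.5% | 1.6% | 2.2% | 2.3% |

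A repeat run gave CC errors of 13.3%, 4.9% and 1.5%. If staff act half the time, CC gives 5.6% (plan SDs) and 3.9% (equal SDs). The discarded-readings column tests an assumed rule; the plan states none.

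**5. Power at a true difference of 0** (means 88/88), CC against carry-forward: 97.0% and 85.2% with the plan's SDs, 85.4% and 84.6% with equal SDs, 62.5% and 82.1% with swapped SDs. With all walks complete it is 82–84%. The 97.0% is not a gain: the CC estimate is biased to +0.49.

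**6. Where carry-forward fails.**
- Linear fall, 27–35% of Mobi walks stopped: error 4.9% (plan SDs), 3.5% (equal), 2.5% (swapped).
- Stops unrelated to SpO2 on 5–20% of Mobi walks only: CC stays at 2.2–2.8%, while carry-forward gives 2.6–4.9% (exponential fall) and 4.0–11.7% (linear fall) across two runs, because an early, high reading fills the rest of the walk.
- Means at 78.3 (Mobi) and 80.3 (cylinder), every sub-80 walk stopped: about 91% of walks stop, both scores are pinned near 80, the estimate is −0.41 and false non-inferiority is 100%. CC is not estimable there either.

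**The case against.** The strongest case against is that nothing shows such stops will be common, or more common on Mobi. Termination is discretionary. Rested walks count as complete, and Section 9.1.1 lets participants sit until stable. Section 7.2.1.1 titrates Mobi to at least 90% and requires a resting SpO2 of at least 90% before each walk. An ITT sensitivity analysis is planned. All of this stands, and it limits the likely size. It does not remove the dependence of CC on the outcome: the 90% condition applies at rest, and the ITT analysis has no defined value for a stopped walk.

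Three stronger readings are tempting, and the documents support none of them.

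- A reader might infer that the plan favours Mobi. At Section 10.4's own means, the chance of a walk mean below 80 is Φ((80 − 80.3)/2.2) ≈ 45% for the cylinder and Φ((80 − 82.3)/3.5) ≈ 26% for the concentrator, which is the opposite imbalance. Those means come from a study that the reference list places in interstitial lung disease, so they need not apply here in either direction.
- A reader might infer that the ITT analysis discards pre-stop readings and so breaks MAR. The text does not say what happens to them.
- A reader might infer that stop time and reason go unrecorded. They are absent from the Section 7.2.2 list, but the contents list names case-report-form and data-management sections and appendices that are not in the public text.

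That a walk ended by staff is incomplete is the natural reading of Section 10.2, not an explicit statement. Section 10.2 mentions a missed second walk as one possibility; it does not rule out a stopped first walk.

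A further objection is that one carry-forward rule for every stop would add bias. Step 6 of the working shows this is right, and the fix allows for it.

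**Conclusion.** The concern holds as a conditional one and should be fixed. CC can exclude a participant because of a low primary outcome, and the ITT analysis does not repair this: it is not primary, the imputation methods it refers to are absent from Section 10.9, and stopped walks have no score.

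If low-SpO2 stops are more frequent on Mobi, false non-inferiority exceeds 2.5%: about 13% (plan SDs) or 5% (equal SDs) in the within-walk illustration with every sub-80 walk stopped, and less if staff act only sometimes. If cylinder stops are more frequent, the test can be conservative (1.5%). If stops are unrelated to SpO2, CC is not biased by them.

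Confidence is high in the mechanism and in the missing rule. Size and direction in this trial are unknown: the figures rest on assumed means, fall shape and staff behaviour. The 5% drop-out allowance in Section 10.4 is justified by both tests falling in one visit, and it is not a stop rate.

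**What to change.** In Sections 10.2, 10.3 and 10.9:

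1. Make the plan's existing ITT set primary, using the Section 10.3 mixed model.
2. Pre-specify the score by reason for the stop. For a walk stopped because of low SpO2, use the mean from start to minute 6 with the last reading before the stop carried forward. Treat a walk stopped for a reason unrelated to SpO2, or never started, as missing and handle it in the mixed model under MAR. State in advance how a distress stop with low SpO2 is classed.
3. Keep as sensitivity analyses: CC, the mean of readings up to the stop, and a worse-value score for low-SpO2 stops.
4. Report stopped walks by device, period and reason.
5. Confirm that SpO2 readings up to a stop, the stop time and the reason are saved.
6. Replace Section 10.2's reference to imputation methods with this rule.

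The cost is wording, at most two data fields, and a check that oximeter readings are stored. SpO2 is already monitored continuously (Section 3.3.1).

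The plan should state the downsides. Carry-forward is an assumption. It only partly corrects a steadily falling SpO2 (about 5% error in the linear case with the plan's SDs). It compresses differences if walk means lie near 80%. It must not be applied to stops unrelated to SpO2. Because Visit 1 must be a single visit, a session stopped in the first walk may leave one walk only; carry-forward error in the exponential case is then 3.5% (plan SDs), 2.8% (equal) and 2.2% (swapped). No change to the walk-stopping rules is proposed.

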#### 4.2.2 Secondary endpoints

- Distance covered during the 6MWTs.
- Post-6MWT SpO2
- Time spent  $\geq$  90% SpO2 during 6MWT
- Participant acceptance questionnaire around ease of use and other aspects specific to portable oxygen use
- Dyspnea and fatigue levels measured by Modified Borg scale (mBorg)

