### 7.2.3 Post 6MWT

Post each 6MWT, participants will record

- Respiratory rate
- Pulse (beats per minute)
- Post-walk dyspnea and fatigue levels measured by the Modified Borg scale

Before the next 6MWT, participants will rest for at least 1 hour breathing their supplemental oxygen device prior to switching to the alternate device for the second test.

After each of the two 6MWTs, participants will complete a participant acceptance questionnaire involving questions about ease of use and other aspects specific to portable oxygen use.

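### Limiting every secondary endpoint to participants who complete both walks discards observed data from stopped walks, and biases the walk-distance comparison if stop rates differ between devices

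*Combined protocol and SAP*

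**What the plan says.** Section 10.2 defines two populations. ITT is "all patients who meet the inclusion/exclusion criteria and begin the first 6MWT". Completed Cases (CC) is "all patients in the ITT population who complete both the first and second 6MWTs". Resting is compatible with completion, but "if the participant stops completely then the 6MWT will be considered incomplete". For the secondary endpoints the rule is "All secondary endpoints will be generated using the CC population".

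The ITT population returns for efficacy in one place only: "A sensitivity analysis of the primary endpoint will be generated for the ITT population". Section 10.9 repeats this ("A sensitivity analysis will be done using the ITT population and a mixed-effects cross-over analysis") under a paragraph that names only the primary endpoint. Section 10.7 gives the secondary endpoints a cross-over ANOVA with random subject effects and 95% confidence intervals. It names no other population, gives no rule for stopped walks, and asks for no count of stops.

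The secondary endpoints in section 4.2.2 include "Distance covered during the 6MWTs". Section 7.2.2 has distance measured in each walk. Section 7.2.3 lists, for each walk, "Post-walk dyspnea and fatigue levels measured by the Modified Borg scale", and places the acceptance questionnaire after each of the two walks.

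**The concern.** For distance, a stopped walk is not a missing value: the distance covered is the distance at the stop. The CC rule nevertheless deletes that walk, and also the participant's other walk, even when the other one was completed. Someone who stops the first walk and completes the second is lost as well. With no ITT analysis of secondary endpoints, these values enter no planned efficacy result.

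The loss is not random. Section 7.2.2 lets staff end a walk on low saturation, with below 80% as its example, and section 9.1.1.3 stops the session on signs of distress. Both are closely related to what the secondary objective in section 4.1.2 evaluates: experience, dyspnea and distance. If more participants stop on one device than on the other, the completers' comparison of distance hides that device's disadvantage.

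**Working it through.** **The plan's own figure.** The documents state no number for the secondary endpoints. The only sample-size figures are for the primary endpoint (section 10.4), and they reproduce:
- SD of the difference = sqrt(3.5² + 2.2² − 2 × 0.2 × 3.5 × 2.2) = 3.74, as stated.
- Power at n = 30 (noncentral t, one-sided 0.025, margin 2, true difference 0) = 80.7% with 28 df. At n = 29 it is 79.3%, so 30 is the smallest n that reaches 80%.
- 30 / 0.95 = 31.6, rounded up to 32. The 5% allowance equals 0.05 × 32 = 1.6 participants.

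Nothing below changes these figures.

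**What happens to one stopped walk**

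| Item | Collected | Enters a planned efficacy analysis? |
|---|---|---|
| Distance in the stopped walk | Each walk (7.2.2) | No |
| Borg and questionnaire after it | Each walk (7.2.3); collection after a stop is implied, not stated | No |
| Same items from the participant's other walk | Yes, if done | No |
| Mean SpO2 (primary endpoint) | Yes | ITT sensitivity analysis only |

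**Size for distance, both walks done.** All inputs except N = 32 are assumed. The devices are otherwise equal, and k participants stop on Mobi at 150 m against 300 m on the cylinder. CC removes all k, so its difference is 0 m. With everyone included the difference is k × (150 − 300) / 32:
- k = 1: −4.7 m
- k = 2: −9.4 m
- k = 3: −14.1 m
- k = 4: −18.8 m

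**Size for distance, second walk missing.** Suppose the k stoppers were all Mobi-first and had no second walk. The section 10.7 model (treatment and period fixed, participant random) then has one short walk per stopper and assigns much of the shortfall to the participant. Without the period term the estimate is (1 − ρ) × k × (−150) / 32, where ρ is the within-person correlation of distance. For k = 1 and ρ = 0.5 this is 0.5 × (−4.69) = −2.3 m. Generalised least squares with the period term and ρ taken as known gives:

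| k | ρ = 0.5 | ρ = 0.7 | ρ = 0.9 |
|---|---|---|---|
| 1 | −2.4 m | −1.5 m | −0.5 m |
| 4 | −10.5 m | −6.4 m | −2.2 m |

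**Dependence on stop rates.** Assume a mean of 300 m, both walks done, a stopped walk losing 25% to 50% of its distance, and stops independent of everything else. The expected all-data difference is −300 × loss × (Mobi stop rate − cylinder stop rate), and the number kept in CC is 32 × (1 − Mobi rate) × (1 − cylinder rate).

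| Mobi / cylinder stop rate | All observed data | CC | Kept in CC |
|---|---|---|---|
| 5% / 5% | 0 m | 0 m | 28.9 |
| 10% / 3% | −5.3 to −10.5 m | 0 m | 27.9 |
| 20% / 5% | −11.3 to −22.5 m | 0 m | 24.3 |
| 5% / 20% | +11.3 to +22.5 m | 0 m | 24.3 |

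A simulation with between-person SD 80 m and within-person SD 30 m (both assumed) agreed to within sampling error. The bias needs unequal stop rates and can run either way.

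**The case against.** The case on the other side has several parts.

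- **Direction.** A reader might infer that the rule favours Mobi, or that it flatters one device on dyspnea and acceptance too. The documents support neither. They give no stop rate for either device. An early stop can mean less exertion and hence a lower Borg score, and nothing shows which way acceptance would move. Only distance has a clear direction, and only when stop rates differ. This objection stands.
- **Pairs may not exist.** Under section 9.1.1.3 a participant in distress has the session stopped and goes back to their own oxygen device, so a first-walk stopper may have no second walk. The mixed model then recovers only part of the effect, as the second calculation shows. This stands and limits the remedy.
- **Stops may be rare.** Resting is allowed, and the plan assumes 5% dropout. One might infer the opposite from section 10.4: under normality its planning values put mean SpO2 below 80% in about 26% of concentrator walks and 45% of cylinder walks. That is not a predicted stop rate. Termination is discretionary, and the source study was in interstitial lung disease (reference 26). How frequent stops will be is simply unknown.
- **Collection after a stop.** The wording about each walk implies that Borg and the questionnaire are still taken, but no section says so for a terminated walk. This stands for those two items; distance does not depend on it.
- **Low stakes.** Secondary endpoints are estimated with 95% confidence intervals and carry no hypothesis, margin or alpha. Stops involving an adverse event still appear in the section 10.8 listing. This limits the severity, but a listing is not an efficacy summary.

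None of this supplies a reason to leave observed distances out of every efficacy analysis.

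**Conclusion.** The point holds in a conditional form. Following section 10.2 exactly, one stopped walk removes both of that participant's walks from all secondary analyses, the removal depends on outcome, and no sensitivity analysis restores the data. If stop rates differ between devices, the distance comparison is biased towards the device with more stops. If they are equal there is little net bias. For Borg and acceptance the data loss is real where values were recorded, but the direction of any bias is not established.

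The documents do not fix the size. For 1 to 4 stoppers on one device and the assumed 150 m against 300 m, CC hides 4.7 to 18.8 m where both walks exist. Where the second walk is missing, the proposed analysis would reveal about 0.5 to 2.4 m for one stopper and 2.2 to 10.5 m for four, at assumed correlations of 0.9 to 0.5. The primary analysis, N and power are unaffected. The change is worth making because it is cheap, but the primary conclusion does not turn on it.

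**What to change.** In sections 10.2 and 10.7:

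1. Analyse the secondary endpoints in all participants who begin at least one walk. For distance, use the distance at the stop. For Borg, the questionnaire and SpO2, use the values recorded at or after the stop where available. Interpret time at or above 90% SpO2 against the time actually walked.
2. Fit the random-subject cross-over model already in section 10.7, so that participants with one walk contribute.
3. Keep the CC analysis as supportive.
4. Tabulate stopped walks by device and period, so that readers can see whether stop rates differ.
5. Confirm in section 7.2.3 whether Borg and the questionnaire are recorded after a stopped walk.

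The cost is SAP wording, one more run of a planned model and one table. The downside is that for participants with only one walk the estimate relies on the mixed model under missing at random and recovers only part of a device effect. The stop table is therefore needed alongside it.

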### 10.3 Statistical Analysis of the Primary Endpoint

The primary hypothesis will be tested using a cross-over Analysis of Variance test (ANOVA). Specifically, a repeated-measures ANOVA with fixed treatment and period effect and random participant effects will be fit to the data. The mean difference between treatment effects will be compared to a non-inferiority margin of -2%, using a Wald test. Additionally, the 97.5% lower one-sided confidence bound for the mean paired difference in mean SpO2 between the Mobi device and the Control device will be calculated.

### 10.4 Justification of Sample Size

Based on a study by Khor et al., evaluating the clinical effectiveness of the Inogen One G2 device compared to Continuous Oxygen Cylinder, the observed mean (standard deviation) in mean SpO2 during the 6MWT was 82.3% (3.5) for Inogen and 80.3% (2.2) for continuous oxygen. For estimating the SD of the difference, we assume that the SD for the Mobi device will be similar to the Inogen One G2 results. The within patient correlation is assumed to be small,  $r=0.2$ . The standard deviation of the difference is 3.74, estimated using the following formula:  $\text{sqrt}(\text{SD}_1^2 +$

$SD2^2 - (2*r*SD1*SD2)$ ), where SD1 and SD2 are the standard deviations for each study treatment and r is the correlation between the repeated measures (within a participant).

Assuming a standard deviation of the difference is 3.74, a true mean difference between treatments of 0, and one-sided significance level of 0.025, a sample size of 30 provides 80% power to detect non-inferiority when the non-inferiority margin is -2.0. This sample size was generated using the Non-Inferiority Tests for the Difference Between Two Means in a 2x2 Cross-over Design procedure, PASS Version 2019 software. Since both treatments will be completed during the same visit, a small drop-out rate is assumed at 5%. Thus, a total of 32 (30/0.95) participants will be enrolled in the study, each participant randomized with respect to the order of treatment.

### 10.5 General Statistical Analysis Guidelines

Descriptive statistics will be used to summarize both continuous and categorical endpoints. The number of observations, mean, median, standard deviation, standard error, minimum and maximum will be calculated for continuous variables, unless otherwise stated. The number of significant digits reported will be as follows: minimum and maximum will have the same number of significant digits as the raw data; the mean, median, standard deviation, and standard error will be reported with one more significant digit than the raw data. Frequencies and percentages will be calculated for categorical data using one significant digit for percentages.

